## - Definitions:

Adverse events will be coded according to Medical Dictionary for Regulatory Affairs (MedDRA) and coded as treatment emergent (TEAE) / non-treatment emergent (non-TEAE) according to the following definitions. TEAEs are defined as events occurring on or after the day of first dose intake of study product and up to follow up visit. Additionally, events present before the first dose of study product, but worsening under treatment are considered as TEAEs. Although every effort will be made to establish the onset date and time, events with missing onset date will be considered as TEAEs. An AE that will not qualify as a TEAE will be considered as a Non-TEAE. Non-TEAES will be summarized separately from TEAES, and will be presented in the same manner as TEAES.

### - **Treatment Emergent Adverse Events**

A given TEAE will be counted once only per patient. The percentages will be calculated in relation to the population exposed (i.e., safety population). All TEAEs will be analyzed, irrespective of their causal relationship with lanifibranor. Recapitulative tables will be provided, showing the following:

- count of exposed patients,
- count and percentage of patients with at least one TEAE,
- count and percentage of each TEAE: TEAEs will be sorted by decreasing order of organ system frequency then by decreasing order of preferred term frequency,
- count and percentage of each TEAE, not taking into account organ system.

In addition, TEAEs will be described according to their time to onset with same categories as for duration of exposure, their maximal intensity and their relationship to lanifibranor, gender and age of patient, time from first intake, outcome, seriousness criteria, corrective treatment, duration, treatment received and action taken. Patient data listings will be provided for all AEs, TEAEs, AEs leading to study discontinuations and SAEs.

Deaths and Serious Adverse Events Incidence of SAEs (irrespective of their emergence classification and relationship to lanifibranor) and deaths will be listed and summarized.

### - **Adverse Events leading to treatment discontinuation**

Adverse event leading to discontinuation of the study will be tabulated, irrespective of their emergence classification and irrespective of their relationship to lanifibranor.

#### 9.7.3 *Other Observations Related to Safety*

### - **Laboratory tests**

The analysis will include patients exposed to study medication who have at least one laboratory test performed after the first study product intake and, when required by the definition of the abnormality, with an available baseline value and available normal ranges. For these descriptions, the baseline value will be the latest available measure before the first study product dose intake. International units will be used in all listings, tables and graphs. Results and changes from baseline of laboratory parameters will be summarized by mean, standard deviation, median, minimum and maximum at each time point and for the final on-treatment visit. Unscheduled and/or repeated results will only be listed and not summarized.

Shift tables and other tabular and graphical methods will be used to present the results for tests of interest. Listings will be provided with flags indicating clinically significant out-of-range values, clinically non-significant out-of-range values.

In addition, out-of-range values will be assessed by the investigator as clinically significant or not clinically significant. Abnormal laboratory tests assessed by the investigator as clinically significant will be reported as an AE.

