#### 5.3.7 *Unscheduled/safety Visits*

During the all treatment and the follow-up period, the Investigator may conduct unscheduled visit that may perform again study procedures, including vital signs assessments, blood sample taken and physical examination. These visits will have to be motivated by the Investigator in the aim of guarantee the safety of the patients.

Specific events listed bellow, will automatically generate an Unscheduled/safety visit:

- ALT increase of 2 times of the baseline value at V0: A safety visit has to be performed 15 days later. A blood taken will be performed to check the ALT level.
- ALT increase of 5 times the upper limit of the normal range (ULN): A safety visit has to be performed 15 days later. A blood taken will be performed to check the ALT level

Please refer to paragraph 10 for withdrawal criteria.

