## **10. Patient Withdrawal & Replacement**

### **10.1 Patient Withdrawal**

Participation in the study is strictly voluntary. The patients have the right to withdraw from the study at any time for any reason, without the need to justify. The Investigator also has the right to withdraw patients in case of safety concerns, protocol deviations or administrative reasons. Since an excessive rate of withdrawals can render the study uninterpretable, the unnecessary withdrawal of patients must be avoided.

Reasons of withdrawal include, but are not limited, to the following:

- Patient decision
- Lost to follow-up, death

- Any AE, laboratory abnormality or illness which, in the opinion of the Investigator, indicates that continued treatment with study therapy and participation in the trial is not in the best interest of the subject.
- Major protocol deviation: e.g. lack of compliance with scheduled visits, non-compliance with study treatment, treatment with prohibited medication during the study (see 22)
- Any deterioration in cardiac status
- ALT or AST > 8 x ULN; or if ALT or AST > 5xULN for more than 2 weeks; or if ALT or AST > 3xULN and bili (total) > 2xULN (or INR>1.5); or ALT or AST > 3xULN and symptoms (Right Upper Quadrant pain, nausea, ...)
- Investigator's decision for any other reason

If a patient discontinues the study, the Investigator will make reasonable efforts to obtain the reason and to perform all protocol-defined end of study assessments as soon as possible. The reason and circumstances for premature discontinuation (e.g. consent withdrawal, AE, lost to follow up, etc.), and the date of withdrawal must be documented in the eCRF. If a patient discontinues the study for safety reasons, the outcome must be known.

In the case of withdrawal due to pregnancy (see paragraph 6.2.1), the patient will be followed until outcome, i.e. at least on a quarterly basis for follow-up evaluation of the pregnancy, foetus, delivery and new born. In the case of withdrawal due to an AE the patient will be followed until resolution of the AE, or until in the opinion of the Investigator the event has stabilized, and the patient is referred to their primary physician for appropriate management of the ongoing event. Reasonable efforts will be made to contact a patient who fails to attend any follow-up appointments, in order to ensure that he/she is in satisfactory health.

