###### All other procedures:

Only observed cases within 3 days after study treatment last intake will be used:

- Missing data will remain missing
- Will also be considered as missing any data collected more than 3 days after study treatment last intake

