###### Note:

- Data collected at Visit 3 being an early treatment discontinuation, should not be taken into account for Week 24 (i.e. actual V3) data descriptions
- For OCUT analysis where data available at Week 28 (i.e. V4) should be described, all Week 28 (i.e. V4) data that are within 4 weeks  $\pm$  2 weeks compared with Week 24 (i.e. V3) are to be taken into account.  
Data collected at Visit 4 being the visit following an early treatment discontinuation, should not be taken into account for Week 28 (i.e. actual V4) data descriptions
- For all analysis based on biopsy data, data collected at actual V3 should be taken into account as well as data collected at Visit 3 being an early treatment discontinuation.

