#### - Descriptive analysis

Fasting glucose and HbA1c assessed at Screening, Baseline, Week 4, Week 14, Week 24 and Week 28, as well as insulin, C-peptid, fructosamide and HOMA index assessed at Week 0 and Week 24, will be described over time using descriptive statistics by treatment group and diabetic status, in terms of:

- Raw values
- Absolute change from baseline

The 95% CI of the mean will also be provided.

- Status over time (Normal-Normal, Normal-Abnormal, Abnormal-Normal, Abnormal-Abnormal)

The 2 timepoints prior to first intake will have to be analysed: screening and baseline.

One graph will also be provided describing the raw values (with 95% CI) by treatment group over time (including screening values)

The HOMA index will also be described qualitatively over time using descriptive statistics by treatment group and diabetic status (HOMA < 3, ≥ 3).

- Absolute changes in HbA1c value will be described qualitatively over time using descriptive statistics by treatment group and diabetic status:
  - o Decrease of HbA1c (Decrease of 1%, No change (Change within ]-1% ; 1%[]), Increase ≥ 1%).
  - o Decrease of HbA1c (Decrease ≥ 0.5%, No change (Change within ]-0.5% ; 0.5%[]), Increase ≥ 0.5%)
- Evaluation of treatment effect (each dose versus placebo)

For fasting glucose, HbA1c, insulin and HOMA index, in order to evaluate each treatment dose versus placebo at week 24, a MMRM will be performed as detailed in section 4.1.5.

In order to take into account multiplicity of tests, the ascending Hochberg procedure will be applied (see section 4.1.5 for details).

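### The plan defines no by-arm count of patients who meet the protocol's own liver stopping limits, and its by-visit rules leave out the rechecks that one of those limits depends on

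*Protocol*

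**What the plan says.** **The limits.** Protocol 10.1 lists among the reasons for withdrawal: "ALT or AST > 8 x ULN; or if ALT or AST > 5xULN for more than 2 weeks". It adds ALT or AST above 3xULN with total bilirubin above 2xULN or INR above 1.5, and ALT or AST above 3xULN with symptoms. Protocol 5.3.7 adds a trigger for extra sampling: "ALT increase of 5 times the upper limit of the normal range (ULN): A safety visit has to be performed 15 days later".

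**How liver tests are summarized.** SAP 5.2.3.9 handles ALT, AST, GGT, alkaline phosphatase and total bilirubin within the efficacy section, at Screening, Baseline and Weeks 4, 14, 24 and 28. It borrows the descriptive method of SAP 5.2.3.8: raw values, change from baseline, and "Status over time (Normal-Normal, Normal-Abnormal, Abnormal-Normal, Abnormal-Abnormal". ALT, AST and GGT also get model-based comparisons of means. The safety laboratory list in SAP 5.3.3.3 includes INR but no transaminase or bilirubin.

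**Which samples enter the summaries.**
- Protocol 9.7.3, Laboratory tests: "Unscheduled and/or repeated results will only be listed and not summarized".
- SAP 4.5.6.3 uses the first non-missing post-dose value when a parameter is retested.
- SAP 4.1.6.3, observed cases under treatment: "Will also be considered as missing any data collected more than 3 days after study treatment last intake".
- The note to that section: "Data collected at Visit 3 being an early treatment discontinuation, should not be taken into account for Week 24 (i.e. actual V3) data descriptions" and "Data collected at Visit 4 being the visit following an early treatment discontinuation, should not be taken into account for Week 28".

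**Partial cover.** Protocol 9.7.3 promises a summary for the last on-treatment visit and listings flagged for clinical significance. It also says: "Shift tables and other tabular and graphical methods will be used to present the results for tests of interest". The tests of interest are not named.

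**The concern.** Safety is part of the study objective, and protocol 6.3 calls every safety variable primary. The protocol also fixes objective liver limits at which a patient should stop. A reader of a dose-ranging study would expect to see how many patients on placebo, 800 mg and 1200 mg reached each limit.

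The planned summaries do not supply that number. A by-visit table gives mean, SD, quartiles and extremes. The four-way status says only inside or outside the laboratory range. The samples that would confirm a sustained elevation are unscheduled, and so are listed only. The SAP does use size categories elsewhere: QTcF and heart rate (4.5.6.4), weight change (5.3.3.4) and HbA1c change (5.2.3.8). Liver tests carry explicit stopping rules and have none.

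**Working it through.** The plan gives no figure to reproduce here. The check sets its rules against each other, with some arithmetic for size.

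**1. Does the status show size?** SAP 4.5.1 defines Abnormal-Abnormal as a baseline outside the range with at least one later value outside it. Entry allows ALT below 10xULN (protocol 4.2.1). A patient going from 1.5 to 8xULN and one going from 1.5 to 1.2xULN both fall in that category.

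**2. Can scheduled visits show more than two weeks above 5xULN?** On-treatment visits after the first dose are at Weeks 4, 14 and 24, each with a window of 3 days either side.
- Planned gap: 10 weeks = 70 days.
- With both windows: 70 - 6 = 64 to 70 + 6 = 76 days.
- Against 14 days: 64/14 = 4.6 to 76/14 = 5.4 times the limit.

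Weeks 24 to 28 are four weeks apart, but Week 28 is off treatment. The recheck at 15 days is the sample that fits the limit (15 > 14). It is unscheduled and so listed only. It is also specified for ALT alone, so AST duration depends on whether AST was drawn.

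**3. Trace of one patient (assumed ALT of 6xULN at Week 4).**
- Week 4 value: scheduled and on drug, so it stays in the Week 4 row.
- Recheck 15 days later: listed, not summarized. If still above 5xULN, the limit is met and the patient is withdrawn. Nothing in 5.3.7 requires dosing to stop at the trigger, so the patient may still be on drug at the recheck.
- Early Visit 3: barred from the Week 24 row. If drawn on drug, it could enter the protocol's last on-treatment summary, which the SAP does not carry over.
- Visit 4 after that: barred from the Week 28 row.

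A patient who first crosses a limit at a per-protocol Week 24 visit still has a Week 28 row. The loss of rows therefore concerns patients who stop early.

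**4. What could a by-visit table show?** SAP 3.5 gives 247 randomised; an even split is assumed: 247/3 = 82.3, so n = 82. Q3 is the 62nd ordered value (0.75 x 82 = 61.5). That leaves 82 - 62 = 20 patients above it, of whom only the largest value is shown.

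Illustration with invented values: 78 patients are the same in two arms (all below 3xULN, mean 1.0, SD 0.3). The other four are 8.5, 2.5, 2.5, 2.5xULN in arm A and 8.5, 7, 6, 5.5xULN in arm B, all above Q3.
- Median, quartiles and maximum agree.
- Means: (78 + 16)/82 = 1.15 and (78 + 27)/82 = 1.28, a difference of 11/82 = 0.13xULN.
- SD, as the square root of [77 x 0.3² + 78 x (1.0 - mean)² + squared deviations of the four]/81: 0.92 and 1.31.
- Above 5xULN: 1/82 = 1.2% and 4/82 = 4.9%.

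The SD would show that the arms differ. It would not say how many patients crossed a limit.

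**5. A zero count is also informative.** For 0/82, the exact two-sided 95% upper limit is 1 - 0.025^(1/82) = 4.4%.

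**The case against.** The best case for the plan has four parts.

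- **The sampling rules are coherent.** Keeping unscheduled values out of by-visit statistics, off-drug values out of an on-treatment summary and early-exit values out of Week 24 is normal practice. This stands: those rules should remain. What is missing is a separate table beside them.
- **Other by-arm routes exist.** Clinically significant abnormalities become adverse events (protocol 6.3, 9.7.3). Events leading to permanent discontinuation are tabulated by arm (SAP 5.3.2.2). The DSMB sees main laboratory results by coded arm (protocol 6.4.3). This stands in part. The event route rests on investigator judgement and is arranged by MedDRA term. The discontinuation reasons in SAP 5.1.1 have no liver-limit category. DSMB output is analysed under a separate plan (SAP section 2).
- **Some later values may be summarized.** The last on-treatment summary could take an on-drug early Visit 3, and SAP 5.1.1 splits Visit 3 into early-termination and Week 24 visits. This stands as a possibility. However, the first would give distribution statistics only, and the second sits under disposition with no matching row in the liver-enzyme table.
- **The table layouts are in an appended mock-up document that was not available.** This stands, and it limits the conclusion to what the two documents state.

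A reader might infer that liver data from withdrawn patients are lost, that none of their later samples can appear in any summary, or that limit crossings cannot be found in the report. The documents support none of these: all values are listed with flags, a crossing at a scheduled on-drug visit stays in its row, and the routes above remain.

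**Conclusion.** The concern holds as a modest reporting gap that is cheap to close. Neither document's analysis text defines a by-arm count of patients at the 10.1 limits or at any multiple of ULN. The stated rules also keep out of the by-visit summaries the rechecks on which the two-week limit depends.

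In size, the question is one of a few patients among about 82 per arm, such as 1.2% against 4.9% in the invented example. How often peaks occur only off schedule cannot be computed from the documents. The conclusion assumes an even split of the 247 randomised and that the mock-ups do not already contain such a table. It does not touch the primary efficacy analysis.

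**What to change.** Keep the by-visit tables on scheduled values. Add to SAP 5.3.3.3 one by-arm table in the safety set. It should give each patient's worst ALT, AST, total bilirubin and INR from first dose to 28 days after last dose (the SAP's treatment-emergent window). Use every sample: scheduled, unscheduled, repeat and early-discontinuation. Count patients with:

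- ALT or AST above 3x, 5x and 8xULN;
- ALT or AST above 5xULN for more than two weeks, where rechecked;
- ALT or AST above 3xULN with total bilirubin above 2xULN or INR above 1.5.

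The symptom-based limit can be reported from adverse event data. Show the baseline category, because entry allows ALT below 10xULN and so overlaps the 5x and 8x limits. Show the number of unscheduled samples by arm. Declare the addition in SAP 4.6.

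The cost is one SAP paragraph, one table from data already collected and one line in 4.6. There are two drawbacks. Patients sampled more often have more chance of an extreme value, which is why the sample counts are needed. AST duration may not be recoverable for every patient.

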### - **Vital signs and ECG**

Descriptive statistics by time point will be computed on actual values and changes from baseline for vital signs and ECG data. The baseline value is defined as the last measure before study product intake. ECG parameters collected are heart rate, PR interval, QRS interval, QT, QTcB (Bazett) intervals. Descriptive statistics (means, standard deviations, and ranges) and changes from baseline

values for all visits will be provided. The summaries will include patients who have at least one measurement performed after the first study product intake. Results and changes from baseline of the following vital sign parameters will be summarized by mean, standard deviation, median, minimum and maximum at each time point and the final on-treatment visit:

- Heart rate: supine,
- Systolic blood pressure: supine,
- Diastolic blood pressure: supine,
- Weight.

Shift tables and other tabular and graphical methods (plots of mean over time) may be used to present the results for parameters of interest.

Confirmatory–inferential analysis may be done for parameters of interest. Listings will be provided with flags indicating clinically significant out-of-range values, clinically non-significant out-of-range values.

Any ECG modification or change in vital sign compared to screening, considered as clinically significant by the Investigator, will be reported as an AE.

#### - **Physical examination**

For physical examination anomalies will be listed and frequencies tables will be computed.

When considered clinically relevant by the Investigator, any new finding of the physical examination, compared to the screening visit, will be reported as an AE.

#### 9.7.4 *Efficacy Analyses*

##### Primary efficacy analysis

The primary population will be the intent to treat FAS population composed of all randomized subject who received at least one dose.

The primary efficacy endpoint will be a binary variable (responder / non responder) based on the change from baseline to Week 24 of the SAF activity score. Responder is defined as a decrease from baseline to week 24 of at least 2 points of the SAF activity score combining hepatocellular inflammatory and ballooning without worsening of fibrosis.

The primary tests of hypotheses will be the Cochran Mantel Haenszel test stratified on diabetes comparing the high dose to placebo and the low dose to placebo. The ascending Hochberg procedure will be used for adjusting the type one error which is globally set at 0.05 two-sided. The primary measure of the effect size will be the CMH odds ratio with an adjustment for diabetes. Because the odds ratio is not easy to interpret when the rate of responders in the placebo group is not very small the odds ratio (OR) and its confidence interval will be converted in Risk Ratio (RR) using the following formula  $RR = (P_1/P_0) = OR / [(1-P_0) + (P_0 \times OR)]$  (75). The log-binomial model will preferentially be used in the absence of convergence or estimability issue for estimating the effect size with RR.

The primary rule for handling the missing data is to consider non-responders all patients who are not confirmed responders.

The primary handling of centers is to ignore in the primary analysis the center effect because 30+ centers should be involved in the study and the number of empty cells in the breakdown of the site by treatment by stratum table can be large (sparse contingency table).

The primary handling of multiplicity of testing will be done through the Hochberg procedure.

The primary handling of heterogeneity of result across strata will be performed through the Breslow-Day test. If the homogeneity hypothesis is rejected, then the estimate of the difference in percentage points between each dose and placebo along with the 95% C.I. will be calculated within each stratum. If the interaction between stratum and treatment (Breslow Day test) is significant it means that the treatment effect has not the same magnitude in diabetic and non-diabetic patients. In the absence of qualitative interaction there will be no further adjustment of the type one error for multiplicity of testing.

The generalizability of the treatment effect across geographical area will be tested and the statistical strategy will be defined in the SAP once the sample size will be known by stratum and country and before the break of the randomization code.

There is no planned interim analysis for success. However, the DSMB may decide to perform some futility analyses in particular in case of safety concerns.

A series of sensitivity analyses will be performed to assess the robustness of results such as the use of a stratified test (country as a stratification factor), the use of other sets of patients (PP set, Evaluable set, Randomized set, completer set). In case of missing assessment at W24, the patient will be considered a non-responder. A responder is consequently a confirmed responder.

Secondary efficacy analyses:

- NASH improver rates in each dose will be compared to placebo using the Cochran Mantel Haenszel test stratified on diabetes.
- Percent of patients with resolution of NASH in each dose will be compared to placebo using the Cochran Mantel Haenszel test stratified on diabetes.
- Percent of patients with a change in components of SAF score in each dose will be compared to placebo using the Cochran Mantel Haenszel test stratified on diabetes.
- Percent of patients with at least 1-point improvement of fibrosis without worsening of NASH in each dose will be compared to placebo using the Cochran Mantel Haenszel test stratified on diabetes.

Planned exploratory analyses:

- Inflammatory markers (fibrinogen, hs-CRP, alpha2 macroglobulin and haptoglobin levels) change from baseline to end of treatment (week 24) will be compared using GLM with the diabetes and dose as covariates. A mixed model for repeated measures will also be used to compare the time course of the response of each treatment group.
- Transient Elastography and Controlled Attenuation Parameter change from baseline to end of treatment (week 24) will only be described.
- Glucose metabolism (fasting glucose and insulin, HOMA index and, in subjects with T2DM, HbA1c) change from baseline to end of treatment (week 24) will be compared using GLM with the diabetes

and dose as covariates. A mixed model for repeated measures will also be used to compare the time course of the response of each treatment group.

- Main plasma lipids levels (TC, HDL-C, calculated LDL-C, TG and apoA1) change from baseline to end of treatment (week 24) will be compared using GLM with the diabetes and dose as covariates. A mixed model for repeated measures will also be used to compare the time course of the response of each treatment group.
- Adiponectin change from baseline to end of treatment (week 24). Comparison tests and estimates of the difference in the change from baseline will be performed using GLM with the diabetes and dose as covariates. A mixed model for repeated measures will also be used to compare the time course of the response of each treatment group.
- Immunohistochemistry if deemed necessary: change in the semi-quantitative score of ballooning and stellate cell activation from baseline to end of treatment (week 24) will be compared using a Van Elteren rank test stratified on diabetes.

The SAP will provide more details on the presented analyses as well as on other exploratory criteria such as quality of life assessment.

All secondary efficacy analyses will be performed using a mixed model for repeated measures or an ANCOVA model if only one post-randomization measure is available. CMH test stratified on diabetes will be used for qualitative variables.

Exploratory analyses on the biomarkers measurements and other evaluations will be proposed and described in the statistical analysis plan.

The final version of the Statistical Analysis Plan will be issued before freezing of the database the break of the randomization code. Any clarification brought in the SAP concerning handling of data and statistical analyses will prevail over any other interpretations of the protocol unless it is the source of major inconsistencies.

